Patient Participant Recruitment

We will recruit and enroll up to 3,000 adults (≥ 18 years of age) from 16 geographically diverse sites who have been diagnosed with lupus. Recruitment will include men and women of all races/ethnicities.

Advertisements (flyers) may be placed in clinic rooms and in participating site publications. Flyers will contain information about the study, as well as the study coordinators contact information. Depending on each sites clinic structure other recruitment strategies will be implemented such as decision aid information offered on the patient portal, waiting room TV, or a paper-based version of the decision aid mailed to the patient before the visit detailing the study and time demand. Coordinators will review the inclusion and exclusion criteria prior to approaching potential patient participants during their regular clinic visits about being in the study.

Potential patient participants who agree to participate will be given a non-signature consent form detailing the study purpose and procedures. Participants will also be required to sign a HIPPA document, since some personal health identifiers (PHI) may be obtained (medical record number, conversations between patient and physician). Each patient participant will be informed of the study compensation of \$50 at the baseline visit and \$10 for each follow-up visit that is completed. Once the study has been explained, the non-signature consent form read over by the participant, and the HIPPA document is signed, study procedures will begin.

The study investigators and research team will have meetings weekly to monitor site recruitment and to determine any intervention for poor recruitment. In the event a problem is identified by either study site PI or staff, a teleconference/webinar will be scheduled to review the issue. These teleconferences/webinars will include discussions of overall recruitment status and identified barriers to recruitment experienced by the site with the study team.

Patient Retention

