Clinic personnel who agree to participate will be sent the interview questions one-week in advance of the scheduled interview. All clinic personnel (even those who will not be interviewed) will receive an electronic copy of the decision aid and be trained on its use through an educational video. The video will explain what the decision-aid is, as well as suggested methods on how it can be administered to patients in the clinic.

Clinic Personnel surveys will be completed electronically via Qualtrics® (Seattle, WA) and stored for analysis. The semi-structured interviews will be administered over the phone, recorded, and transcribed for analysis in NVivo®.

Specific Aim2: Prior to each site implementing the decision aid; standardized capacity-building activities will be initiated. These activities are as follows:

- Education: A series of 60-minute seminars including all 16 clinics that educates clinic personnel about the decision aid includes its purpose, contents, and supporting evidence.
- Training: A series of webinars, offered 1-2 months after each sites formative evaluation, that describes the clinic-specific findings of the formative evaluation, reviews the implementation strategies available to the clinic (both standardized and tailored), and jointly identifies the preferred strategies for the clinic.
- Technical Assistance: On going, ad hoc technical support on the use and maintenance of the iPad (e.g., trouble launching the DA, problems navigating screens).
- Clinic Champion: - Designated member of clinic who is dedicated to supporting, marketing, and driving implementation of the DA in the clinic.
- Refresher Training Course: A webinar conducted every six months or as needed that describes the

implementation strategies, common barriers being confronted across the 16 participating clinics, and shares best practices of how these strategies are being deployed across the 16 clinics to sustain the intervention.

Tailored Implementation Activities

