Sites will also have the option to choose from recommended Tailored Implementation Activities. These strategies are clinic-targeted and patient-targeted activities designed to stimulate participant recruitment and retention. Sites will choose either activity that is most relevant for implementation of the DA at their clinic and we anticipate that some sites will choose both activities. At the end of the study, all sites will be reviewed to determine with strategies were used throughout the duration of the study.

Clinic-targeted Activities:

- DA reminder in patient intake process
- Audit and feedback
- Team huddles/clinic meetings

Patient-targeted Activities

- Pre-visit web-based portal messages with
 - Access to decision aid via a link
 - Information regarding the study time demand
- Pre-visit delivery of paper-based version of decision aid
- Clinic poster about decision aid
- Decision-aid information through the waiting room TV/online kiosk

The DA will be given to all patient participants that meet the eligibility criteria during their regularly scheduled lupus clinic visit. Before reviewing the decision-aid, patients will view a short educational video on the purpose and use of the decision-aid. Questionnaires and the DA will be administered on an iPad, and questionnaires will take no more than 30 minutes on average, to keep responder burden low. Three and six-month follow-up questionnaires will be administered via phone, mail, or at the regularly scheduled clinic visit per the patient participant preference, and will last no more than 15 minutes.

In the event clinic personnel transition to a different position or leave the organization, they will be given a Clinic Personnel Exit interview* to assess the reason for departure, their view on the dissemination of the decision-aid into normal clinic flow, and the sustainability for future use.

Aim 2 Clinic Personnel Survey

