6.3 Implementation Strategy Fidelity and Adaptation

Study investigators will develop and work with clinic personnel to apply the standardized and tailored implementation activities within the clinic setting. It is expected that strategies will be adapted to suit each clinic's unique context and circumstances. We therefore expect to implement 16 different approaches. We will capture and describe each unique approach and use these findings to inform key outcomes. The periodic check-ins for each site following the Education, Training, and Refresher Training standardized activities will allow study personnel to determine the extent to which the DA has been implemented within clinic flow and processes.

Patient participant study compliance will be measured by completion of all study assessments, including the three and six month follow-up and semi-structured in-depth phone interviews. We will also assess whether or not the patient views the DA at the first visit at baseline and/or requests an electronic or paper copy of the DA (Aim 2).

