the alternative that there is a change over time. For the analytic approach we will examine mean levels (total change) and quantify with means (or proportions, as appropriate) and 95% confidence intervals. We will also examine patterns of change (growth trajectories) while controlling for differences between clinics using multivariable models that account for repeated measures and clinic clustering of patients (i.e., generalized estimating equations (GEE) with robust standard errors). Additional analyses may examine by-group comparisons of clinics determined by clinical characteristics (e.g., geographic areas, clinic type, and patient diversity) observed in Specific Aim 1. Any such by-group analyses will be conducted separately. A primary independent variable of interest is the type of strategy used for implementation. Following completion of the study, each sites strategies will be evaluated and sites will be grouped accordingly. A covariate allowing for testing group differences will be included in the multivariable models to assess whether trajectories differ by implementation strategy.

The second component of our evaluation of Specific Aim 2 will use fuzzy set Qualitative Comparative Analysis (fsQCA) to assess effectiveness of implementation strategies for clinic-level outcomes. fsQCA is a case-oriented approach that examines relationships between conditions (similar to explanatory variables in regression models) and outcomes using set theory to answer the question: “what conditions, alone or in combination, are necessary or sufficient to produce an outcome?” For patient-physician communication analysis, question-asking, assertive responses, and expressions of concern, will be coded as patient participation; supportive talk and partnership building by provider will be coded as active physician communication. Further details are provided in Section 9.4.

Specific Aim 3: Targeted participants for this Specific Aim are the same key clinic informants from Specific Aim 1 and 2 patients per clinic from Specific Aim 2. Similar to Specific Aim 1, the analytic approach is largely descriptive and there are no formal statistical null and alternative hypotheses. Specific descriptive statistics are described in the table below. Further details are provided in Section 9.4.

Specific Aim 3 Data Collection and Analyses		
Data Type	Interview Content	Analytic Methods

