9.4.7 Missing Data and Outliers

The rate of missing values will be evaluated on a variable-by-variable basis. Clinics and/or patients with extensive missing values will be deleted from all analyses. A clinic or patient with a missing value for any variable involved in a specific analysis will be excluded from that analysis only (case wise deletion). There are no plans for imputation of missing values. Theoretical assumptions for all statistical procedures will be evaluated (e.g., evaluation of normality, residual plots, and outlier evaluations). Any outliers will be inspected for data coding and entry errors and they will be corrected whenever appropriate. In the case of true outliers, sensitivity analyses with the specific values removed will be conducted in order to evaluate the robustness of the observed results.

In the event that there is insufficient (or excessive) variation in implementation strategies to create 2 clearly differentiable study groups, alternative definitions of the primary independent variable may be created (e.g., groups determined by number of strategies used or groups determined by percentage of staff trained).

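### The Aim 2 strategy groups are formed after completion from activities used over the whole study, with no rule or lock, so the label can reflect earlier results and be chosen with outcomes in hand

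*Combined protocol and SAP*

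**What the plan says.** Section 9.1 (Specific Aim 2) gives strategy a leading role: "A primary independent variable of interest is the type of strategy used for implementation". It then fixes when the groups are made: "Following completion of the study, each sites strategies will be evaluated and sites will be grouped accordingly". The resulting group covariate enters the multivariable GEE models to test whether trajectories differ between strategies.

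Section 6.1 (Tailored Implementation Activities) sets the exposure window: "At the end of the study, all sites will be reviewed to determine with strategies were used throughout the duration of the study". The tailored activities fall into clinic-targeted and patient-targeted types, and "we anticipate that some sites will choose both activities". Section 6.3 expects adaptation to each clinic: "We therefore expect to implement 16 different approaches".

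An earlier choice exists. The training webinar in Section 6.1, held one to two months after a site's formative evaluation, reviews the available strategies "and jointly identifies the preferred strategies for the clinic". Nothing says that the groups use this choice.

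Section 9.4.7 allows the primary independent variable to be redefined if strategies vary too little or too much to give two distinguishable groups. Its examples are "groups determined by number of strategies used or groups determined by percentage of staff trained".

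**The concern.** A label fixed at the end but applied from month 0 assumes that the strategy came before the results it is meant to explain. Here it need not have done. A clinic that is struggling may add activities, which makes those activities look ineffective. A clinic with spare capacity may add them because things are going well, which makes them look effective. Either way, the contrast mixes what a strategy did with which clinics came to adopt it, and a small-sample correction to the GEE would not remove that.

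The second problem is freedom of choice. With 16 distinct approaches expected, reducing them to two groups needs judgement. The plan places that judgement after outcomes exist and adds alternative definitions without an order. At stake is the credibility of the Aim 2 strategy comparison, and of the fsQCA if it uses the same end-of-study strategy data.

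**Working it through.** **1. Timing.** Table 1 has patient enrolment running from Q2 to Q10, and each patient is followed for six months (Section 8). A patient enrolled in Q2 finishes two quarters later, around Q4. Staff are surveyed at 0, 6, 12 and 24 months. An activity first adopted after Q4 would still define the exposure of that patient and of the month-0 staff survey.

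**2. Routes from performance to strategy.**
- Section 5.8: regular meetings are held "to monitor site recruitment and to determine any intervention for poor recruitment". Section 6.1 describes the tailored activities as aids to recruitment and retention.
- Section 6.1: coordinators are interviewed every six months, and concerns are acted on at the next weekly call.
- Section 6.1: refresher webinars share practice across sites, and audit and feedback is itself a selectable activity.

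**3. Safeguards.** The documents give no grouping rule, no requirement to log adoption dates, no time-varying exposure, no masking of the classifier to outcomes and no lock.

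**4. Illustration of size.** The plan has no figure to reproduce: Section 9.2 gives confidence-interval widths, not power for a strategy contrast. From the documents: 16 clinics, at least 35 patients each, ICC 0.05. Assumed: total SD 1, no true strategy effect, 1–4 activities at launch unrelated to outcome, and clinics in the lower half of early results adding Binomial(2, p) activities. Clinics are split 8 v 8 by final count and compared by a two-sided t-test at 0.05.

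- Variance of a clinic mean: 0.05 + 0.95/35 = 0.077, so SD 0.278.
- Standard error of an 8 v 8 difference: 0.278 × √(2/8) = 0.139.

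| p | Spurious difference in levels | Rejection, levels | Rejection, change (clinics react to low levels) |
|---|---|---|---|
| 0.25 | −0.04 SD | 0.061 | 0.050 |
| 0.50 | −0.10 SD | 0.117 | 0.048 |
| 0.75 | −0.14 SD | 0.182 | 0.057 |

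At p = 0.75 the spurious difference is about one standard error (0.14/0.139). Repeat runs put the levels column at about 6–19%. Launch-count grouping rejects about 5% here, but only because launch choice was assumed unrelated to outcome. With 187 patients per clinic (3,000/16), levels rejection is 0.128 at p = 0.5 and 0.228 at p = 0.75, so more patients do not help. If strong clinics add activities instead, the sign reverses.

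The change column adds a follow-up measure with assumed within-patient residual correlation 0.5 and no variation in clinic slopes. A stable clinic effect u cancels, since (u + follow-up error) − (u + baseline error) contains no u. The remaining bias is +0.01 to +0.02 SD. A clinic slope SD of 0.1 at p = 0.75 gives rejection of 0.056. If clinics instead react to early *change*, rejection for change rises to about 10–15% at p = 0.5–0.75. If additions are unrelated to the outcome, rejection on levels is 0.048.

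**5. Redefinition.** If the tests were independent, picking the best of two definitions gives 1 − 0.95² = 0.0975, and of three 1 − 0.95³ = 0.143. Real definitions overlap, so the inflation would be smaller.

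**6. Does launch choice cure it?** Sections 9.1 and 9.4.2 say that formative findings inform strategy selection. Letting launch count depend on the clinic effect (assumed coefficients 0.3, 0.5 and 1.0) makes launch grouping reject 0.10, 0.16 and 0.40 on levels, with bias −0.09, −0.14 and −0.23 SD.

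**The case against.** The strongest reply is that the error rates for levels describe the wrong contrast. Section 9.1 asks whether trajectories differ, and a stable clinic effect cancels in change. This largely stands: a reader might carry the 6–19% over to the planned test, and the documents do not support that. The plan does not say whether the group term enters as a main effect or as an interaction with time, so levels are not irrelevant, but change is closer to the stated purpose.

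Second, the signal named in Section 5.8 is recruitment, whereas the Aim 2 outcomes in Section 9.4.2 are Likert perceptions, and no interim analysis is planned. This stands in part. Coordinator interviews and audit and feedback could carry other information, but the documents show that results *can* shape strategy, not that they will.

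Third, recording strategies as used is a legitimate implementation question in an observational case study, and fsQCA handles combinations. Agreed. The difficulty is only the use of that record as a fixed explanatory covariate for the whole trajectory.

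Three further inferences are tempting and unsupported:
- **That the implementation manual rests on this comparison.** Sections 6.1 and 8 build it from the Aim 3 interviews.
- **That launch choice is unbiased.** It is informed by clinic readiness and barriers.
- **That the webinar choice is already on file and precedes all enrolment.** Section 6.1 says strategies are identified, not recorded. The formative evaluation spans the first six months, while enrolment opens in Q2.

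**Conclusion.** The point holds in a limited form. A primary independent variable is defined after completion, from exposure over the whole study, with no rule and with open-ended redefinition, while site activities may change in response to performance. The strategy contrast can therefore be biased in either direction, and the groups can be chosen with outcomes in hand.

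The size is unknown. The simulated rates rest on an assumed reaction rate, a clinic-level t-test in place of the GEE, and assumed correlations; they show direction and possible order of magnitude only. On the planned trajectory test, material inflation appears only if clinics respond to early change. The formal Aim 2 null of no change over time does not use the groups and is untouched. This should be corrected, but it does not undermine the study as a whole.

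**What to change.** In the SAP and site procedures:

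1. Record each site's strategy choice from the training webinar, with its date, and define the primary strategy variable from it as two clinic-level indicators: any clinic-targeted activity and any patient-targeted activity.
2. Section 5.8 (Patient Retention) can be read as having every site use a patient-targeted activity. If that is meant, that indicator does not vary, and the clinic-targeted one carries the comparison.
3. Name one fallback now, the number of tailored activities chosen at that point, in place of the open list in Section 9.4.7.
4. Lock the coding before outcome data are analysed.
5. Log the dates of later additions and keep the as-used grouping as a labelled sensitivity analysis.
6. Describe all strategy contrasts as non-causal, since launch choice remains confounded by clinic readiness.

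The cost is SAP wording and minor record-keeping at 16 sites. The downside is some dilution where clinics later change activities, which the as-used analysis would help to show. The change removes reverse causation from later additions and post-hoc grouping; it does not remove confounding.

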9.2 Sample Size Determination

A power analysis for the quantitative portion of Specific Aim 2 was conducted using the following assumptions: (1) 16 clinics and (2) an intraclass correlation coefficient of 0.05. This provided us with a total confidence interval width of 5.3% for 10% of the total clinic population that is administered the lupus DA to a width of 8.1% , if 40% patients are administered the lupus DA. For outcomes on a 5-point Likert scale, the corresponding 95% CI widths for standard deviation of 0.5 and 2.0 on the mean score is estimated to be 0.09 vs. 0.35, respectively. For individual-level outcomes measured as a rate (e.g., # visits/1,000) or as means (e.g., Likert-scale), we anticipate small margins of error. A minimum number of proposed sites (n=16) are needed to comprehensively assess how different implementation strategies are influenced by and interact with different contextual conditions (different geographic areas, clinic type, and patient diversity) to affect implementation effectiveness, and thus, determine the generalizability of the study findings. However, given the proven effectiveness of the DA (original PCORI study), and in the spirit of dissemination and implementation research, we will continue to recruit to our proposed maximum sample size target of 3,000.

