9.3 Populations for Analyses

The analysis population for each Specific Aim is below:

Specific Aim 1

- Key clinic personnel who complete the semi-structured in depth phone interview (6-8 staff per clinic)
- Clinic personnel who complete the online clinic personnel survey (all staff, up to 15 per clinic)
- Using administrative records, sites will report the total number of patients viewing the DA and the total number of patient visits during the active study time frame.

Specific Aim 2

- All enrolled participants who complete the baseline visit, as well as those who complete the three and six month follow-up questionnaires
- Clinic personnel who complete the online surveys

Specific Aim 3

- Key clinic personnel from Aim 1+ 2 patients per site who complete the post-study semi-structured in depth phone interview. (6-8 key clinic personnel + 2 patients per site)
-

The protocol population will be all participants who attend all study visits and complete the trial.

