9.4.2 Analysis of the Primary Efficacy Endpoint(S)

Specific Aim 1:

Qualitative: Emergent theme analysis, within each clinic and based on the CFIR domains, will be initially conducted. These themes will be used to identify the preferred implementation strategies for use in a clinic. These within-case themes also will be used to compare and contrast between clinics to identify unique and common barriers to implementation.

Quantitative: Univariate statistics (means, standard deviations) will be used to describe each clinic's learning environment and readiness to implement change. Spearman correlations will be estimated to assess how different aspects of the clinic's learning environment and readiness to implement change may vary across clinics. Similarly, t-tests and one-way ANOVAs will be estimated to assess how the learning environment and readiness to change varies a

function of clinic characteristics (e.g., location, private vs. academic). Penetration will be assessed by evaluating the proportion of eligible patients reviewing the DA overall and in each site. Simple proportions and 95% confidence intervals will be computed. Patient healthcare utilization outcomes (e.g., inpatient visits and ER/urgent care visits) will be assessed similarly.

The results of the qualitative and quantitative analyses described above will be consolidated to construct a profile or “case study” for each clinic.

Specific Aim 2:

Targeted participants for this aim are (1) age \geq 18 years with a diagnosis of lupus from participating clinics. Objective measures will be assessed in both clinic personnel and in patients. Clinical personnel will evaluate perceived acceptability of intervention measure for the DA, perceived DA implementation success, and perceived DA permanence. All will be assessed on an ordinal scale (strongly disagree = 1) to (strongly agree = 5). Similarly, patients will evaluate perception of DA usefulness, patient satisfaction for the DA, perceived intervention appropriateness measure for the DA, and perceived feasibility of intervention measure for the DA. All of these patient assessments will be measured on a Likert-type scale.

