For individual-level outcomes, initial analyses will focus on how clinic personnel and patient perceptions change over time. We will examine mean levels (total change) and patterns of change (growth trajectories) while controlling for differences between clinics using multivariable models that account for repeated measures and clinic clustering of patients (i.e., generalized estimating equations (GEE) with robust standard errors). The second component of our evaluation of **Aim 2** will use fuzzy set Qualitative Comparative Analysis (fsQCA) to assess the effectiveness of implementation strategies for clinic-level outcomes. fsQCA is a case-oriented approach that examines relationships between conditions (similar to explanatory variables in regression models) and outcomes using set theory to answer the question: “what conditions, alone or in combination, are necessary or sufficient to produce an outcome?”

For patient-physician communication analysis, question-asking, assertive responses, and expressions of concern will be coded as patient participation; supportive talk and partnership building by provider will be coded as active physician communication.

Specific Aim 3:

Similar to **Aim 1**, emergent theme analysis within each clinic will be initially conducted. These themes will focus identify the implementation lessons learned by the clinics, including and especially the implementation challenges faced by the clinic throughout the study, and their opinions of the opportunities and challenges to sustaining use of the DA once the study ends. These within-case themes also will be used to compare and contrast between clinics to identify common lessons learned and ideas for how to sustain the DA moving forward.

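### Sixteen clinics with an ICC of 0.05 cannot give the confidence interval widths stated in Section 9.2: the effective sample size is capped at 320, and the widths need about 474 to 562

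*Combined protocol and SAP*

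**What the plan says.** Section 9.2 (Sample Size Determination) bases the precision of the quantitative part of Aim 2 on two assumptions: "1) 16 clinics and (2) an intraclass correlation coefficient of 0.05". From these it derives four full interval widths. For the share of patients given the decision aid: "This provided us with a total confidence interval width of 5.3% for 10% of the total clinic population that is administered the lupus DA", rising to 8.1% "if 40% patients are administered the lupus DA". For 5-point Likert outcomes, the corresponding 95% width for "standard deviation of 0.5 and 2.0 on the mean score is estimated to be 0.09 vs. 0.35, respectively". It then anticipates small margins of error.

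Section 9.2 gives neither a number of patients per clinic nor a formula for these widths. Elsewhere the plan sets a minimum of 35 patients per clinic (Section 8) and a maximum of 3,000 in total (Sections 5.8 and 9.2).

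On analysis, Section 9.4.2 plans, for perceptions over time, "multivariable models that account for repeated measures and clinic clustering of patients", fitted by GEE with robust standard errors. For uptake it says "Penetration will be assessed by evaluating the proportion of eligible patients reviewing the DA overall and in each site", using simple proportions with 95% intervals.

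**The concern.** With a fixed number of clusters and a positive ICC, adding patients within clusters gives diminishing returns, and the effective sample size has a hard upper limit. The stated widths look too narrow for 16 clusters at an ICC of 0.05, whatever number per clinic was used. The two widths for proportions also do not stand in the ratio that a common sample size requires.

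These are the only numerical precision figures for the quantitative part of Aim 2. A reader would expect tighter single-time estimates than the stated assumptions allow and, with no sample size or formula given, could not trace the discrepancy.

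**Working it through.** **Inputs.** From Section 9.2: k = 16 clinics, ICC = 0.05, full widths 5.3% (p = 0.10), 8.1% (p = 0.40), 0.09 (SD 0.5) and 0.35 (SD 2.0). The 95% level is stated for the Likert widths, and the word linking them to the proportions implies the same level there. From Section 8: at least 35 per clinic, so 16 x 35 = 560. Maximum 3,000, or 187.5 per clinic if equal.

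**Formulas.** Width = 2 x 1.96 x sqrt(V / n_eff), with V = p(1 - p) or SD². With equal clinic sizes m, n_eff = 16m / (1 + (m - 1) x 0.05). As m grows, this tends to 16/0.05 = 320 from below.

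**Step 1: what the stated widths need.** Inverting, n_eff = (2 x 1.96)² x V / width².

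| Stated width | V | n_eff needed | Range allowing for rounding |
|---|---|---|---|
| 5.3% at 10% | 0.09 | 492 | 483-502 |
| 8.1% at 40% | 0.24 | 562 | 555-569 |
| 0.09 at SD 0.5 | 0.25 | 474 | 426-532 |
| 0.35 at SD 2.0 | 4 | 502 | 488-516 |

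Even the lowest value after rounding, 426, is above 320. The plan's figures therefore cannot be reproduced from its own two assumptions for any m.

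**Step 2: what the assumptions give.**

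| | n_eff | 10% | 40% | SD 0.5 | SD 2.0 |
|---|---|---|---|---|---|
| Stated | - | 5.3% | 8.1% | 0.09 | 0.35 |
| Ceiling, unlimited patients | 320 | 6.6% | 10.7% | 0.110 | 0.438 |
| Excess at ceiling | | +24% | +33% | +22% | +25% |
| N = 3,000, design effect 1 + 186.5 x 0.05 = 10.325 | 291 | not given | not given | 0.115 | 0.460 |
| N = 560, design effect 1 + 34 x 0.05 = 2.70 | 207 | not given | not given | 0.136 | 0.544 |

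The proportions are left out of the last two rows because penetration is not measured on the enrolled patients alone, so 560 and 3,000 are not its denominator. The Likert widths are 28% and 31% wider than stated at 3,000, and 51% and 56% wider at 560. These are best cases: equal clinic sizes and z = 1.96. With t on 15 df they become 0.125 and 0.500 at 3,000, and 0.148 and 0.592 at 560.

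**Step 3: do the four widths agree with each other?** At one common sample size, width(40%)/width(10%) = sqrt(0.24/0.09) = 1.63. The stated ratio is 8.1/5.3 = 1.53 (1.50-1.55 after rounding). The other three widths share an n of about 488-501, and n = 500 gives 8.6% at 40%. Wilson, Clopper-Pearson and continuity-corrected intervals give no common n for the two proportions either.

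At 30% the ratio is sqrt(0.21/0.09) = 1.53, as stated. A width of 8.1% at 30% needs n = 15.37 x 0.21 / 0.081² = 492 (486-498), and all four widths then share n of about 488-498. That n is still above 320. At the ceiling the 30% width is 2 x 1.96 x sqrt(0.21/320) = 10.0%, or 24% wider than 8.1%.

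**Step 4: other readings.**
- t on 15 df raises the required n_eff to 561-665.
- At 90% confidence the requirement is 334-396, still above 320, though 0.09 alone could reach 300 through rounding.
- At 80% confidence it is 203-240, below the ceiling, but the text says 95%.
- If the widths were half-widths, the requirement would be 119-141, also below the ceiling. With 30% in place of 40%, 12 patients per clinic would then give all four figures: n_eff = 192/1.55 = 124. But Section 9.2 calls the figure a total width, and the plan's minimum is 35 per clinic.

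**The case against.** The strongest reply is that the ceiling depends on treating clinics as random. The 16 clinics were chosen deliberately for variety (Sections 5.1 and 6.2), and the models are said to control for differences between clinics, so they could be taken as fixed. The variance is then multiplied by 0.95 and there is no ceiling. As printed, three widths fit a total N of about 463-477, while 8.1% at 40% needs 527-541. With 30% all four would agree: 16 x 29 = 464 gives 5.3%, 8.1%, 0.09 and 0.35. This has some force. Against it, Section 9.2 offers the ICC as the basis of the calculation and wants to "determine the generalizability of the study findings", which points to clinics as a sample. Section 9.4.2 also plans for clinic clustering, although that supports the random reading for the perception outcomes only, not for penetration.

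A reader might also infer that the 40% width shows a second, independent failure of the calculation. The documents do not support that: a single wrong digit would account for it. They do not establish the slip either.

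A reader might infer that the planning widths hardly matter because every reported interval will come from GEE. That holds for perceptions. For penetration, Section 9.4.2 plans simple proportions with 95% intervals and does not mention clustering.

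A reader might infer that Section 9.2 names no denominator. It does, the whole clinic population, but this differs from the eligible patients in Section 9.4.2 and from Section 9.3, where "sites will report the total number of patients viewing the DA and the total number of patient visits during the active study time frame".

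**Conclusion.** The concern stands. With 16 clinics as random clusters, an ICC of 0.05 and 95% full widths, no number of patients gives the figures in Section 9.2. The shortfall at the ceiling is 22-33%, or 22-25% if the 8.1% belongs to 30%. The conclusion rests on the standard design effect, since the plan names no formula; unequal clinic sizes, likely under competitive enrolment, would widen the intervals further. The mismatch among the four figures comes from the 40% entry alone, and its cause cannot be settled from the documents.

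The harm is an over-favourable statement of precision. It might be tempting to conclude that the study is too small or its targets wrong. The documents do not support that: Section 9.2 justifies the 16 sites by diversity of context and the 3,000 patients by dissemination, and no decision rule uses the widths. It should be corrected, but it does not undermine the design.

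**What to change.** In Section 9.2:
- Confirm whether 40% or 30% was meant.
- State the number per clinic, the design-effect formula and the confidence level for all four widths.
- Reconcile the penetration denominator across Sections 9.2, 9.3 and 9.4.2 (clinic population, patient visits or eligible patients).
- Recompute all four widths. For single-time patient Likert means (SD 0.5 and 2.0), give about 0.14 and 0.54 at 16 x 35, and about 0.115 and 0.46 at 3,000, labelled best case (equal clinic sizes, z = 1.96). For penetration, give no less than 6.6% at 10% and 10.7% at 40% (10.0% if 30% was meant), with actual figures once the denominator is settled.
- If clinics are meant as fixed, say so and drop the ICC as the basis.

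In Section 9.4.2, state whether the penetration intervals account for clinic clustering, consistent with the ICC basis in Section 9.2.

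The cost is recalculation and rewording, and a less favourable precision statement. No extra patients or procedures are needed, and the GEE analysis does not change. If the penetration intervals are to allow for clustering, that is one added specification in the analysis text.
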